13.14.3 Rehospitalization

Time to rehospitalization and the reason for rehospitalization will be reported. Time in and out of the hospital will be reported for the HM3 and HM II Subjects. Treatments will be compared on time to re-hospitalization using the log-rank test. Subjects not re-hospitalized will be censored at last known follow-up.

13.14.4 Reoperations

Time to reoperation, frequency of reoperation, and the reason for the surgery will be reported for HM3 and HM II Subjects. Treatments will be compared on time to re-operation using the log-rank test. Subjects not re-operated will be censored at last known follow-up.

13.15 Analysis of Functional Status

13.15.1 NYHA

The Subjects NYHA Functional Status will be assessed by an independent assessor at baseline and then at 1, 3, 6, 12, 18, and 24 months. At each visit, treatments will be compared on NYHA functional status and on the change from baseline functional status using the Wilcoxon Rank Sum test. The Short Term indication will be limited to the 1, 3, and 6 month assessments. The Long Term indication will include all assessments until 24 months or outcome, whichever occurs first.

13.15.2 Six Minute Walk Test

Subjects may not be able to walk due to heart failure, especially at baseline. Subjects unable to walk due to heart failure will receive a score of 0 meters. For all other reasons for missing data the score will remain missing and not be included in the analysis. The Six Minute Walk test will be conducted at baseline and then at months 1, 3, 6, 12, 18 and 24 post implant. Data will be analyzed using mixed modeling by comparing the distances walked over time to the baseline distance. The Short Term indication will be limited to the 1, 3, and 6 month assessments. The long term indication will include all assessments until 24 months or outcome, whichever occurs first.

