13.14 Analysis of Secondary Endpoints

Secondary endpoints will each be tested at the two-sided 0.05 level of significance. There will be no adjustment for multiple comparisons across the secondary endpoints. There will be no imputation of missing data for the secondary endpoints.

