16.7 Subject Follow-up Assessments

16.7.1 Clinic Follow-up Post-implant: 30 Days (+/- 7 days) for 1 month assessment, 90 Days (+/- 30 days) for 3 month assessment, and 180 days (+/- 30 days) for 6 month assessment

The Subject must be seen for a clinic visit to assess the following:

1. Current Subject Status: whether or not the Subject is ongoing on VAD support
2. Subject Outcome: whether or not the Subject has been transplanted, or explanted
3. Current medications (total daily dose): anticoagulation/anti platelet, antibiotics, and cardiovascular medications including ACE inhibitors, ARBs, beta blockers, statins, nitrates, allopurinol, aldosterone blockers, and diuretics including metolazone, hydrochlorothiazide and furosemide
4. Vital Signs
5. Laboratory Assessments:
 - a. Hematology: hemoglobin, hematocrit, percent lymphocytes, platelet count, WBC, PHgb, Bleeding/Coagulation: INR, aPTT/PTT, PT
 - b. Chemistry: Potassium, BUN, creatinine, uric acid, sodium, eGFR (calculated), serum BNP or NT-proBNP, total protein, albumin or pre-albumin, CRP or hs-CRP
 - c. Lipids: cholesterol
 - d. Liver Enzymes: LDH, AST, ALT, total bilirubin
6. Echocardiogram : LVEF, LVEDD, LVESD, AV opening, AI, MR, TR including severity and/or grade.
7. Chest x-ray: PA and Lateral (30 Days and 180 Days only)
8. NYHA Classification (determined by an independent assessor defined as an advanced practice practitioner other than the treating investigator)
9. 6 Minute Walk Test (6MWT) (if Subject is able; reason must be provided if not performed)

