4. During the test, the walking pace of the Subject should not be influenced. The test supervisor must walk behind the Subject – do not walk with, rush up behind, or rush past the Subject.
5. Each time the Subject returns to the starting line, record the lap.
6. While walking, encourage the Subject at one minute intervals with the following phrases:

1 minute: YOU ARE DOING WELL. YOU HAVE 5 MINUTES TO GO.
2 minutes: KEEP UP THE GOOD WORK. YOU HAVE 4 MINUTES TO GO.
3 minutes: YOU ARE DOING WELL. YOU ARE HALFWAY DONE.
4 minutes: KEEP UP THE GOOD WORK. YOU HAVE ONLY 2 MINUTES LEFT.
5 minutes: YOU ARE DOING WELL. YOU HAVE ONLY ONE MINUTE TO GO.

7. The Subject should be spoken to only during the 1-minute encouragements; no response should be made to the Subject's questions about the time and distance elapsed.
 - a. If the Subject is not concentrating on the walking, the Subject can be reminded at a 1-minute mark:

THIS IS A WALKING TEST, TALKING WILL UTILIZE YOUR ENERGY RESERVE AND INTERFERE WITH YOUR PERFORMANCE.

7. When only 15 seconds remain, state:

IN A MOMENT I AM GOING TO TELL YOU TO STOP. WHEN I DO, STOP RIGHT WHERE YOU ARE AND I WILL COME TO YOU.

9. When the timer reads 6-minutes, instruct the Subject to STOP and walk over to him/her. Consider bringing a chair if the Subject appears exhausted. Mark the spot where the Subject stopped.

If the Subject wishes to stop walking during the test

If the Subject is slowing down and expresses that he/she wants to pause, keep the timer running and state:

REMEMBER, IF YOU NEED TO, YOU MAY LEAN AGAINST THE WALL UNTIL YOU CAN CONTINUE WALKING AGAIN.

If the Subject wishes to stop before the 6-minutes are complete and refuses to continue (or you decide that he/she should not continue), provide a chair for the Subject to sit on and discontinue the test. Record the distance completed, the time the test was stopped and the reason for pre-maturely stopping.

Immediately after the test

1. Total the number of completed laps and add the additional distance covered in the final partial lap. Record the distance walked to the nearest meter.
2. Observe the Subject sitting in a chair for at least 10 minutes after the test is completed.

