APPENDIX 5: MODIFIED RANKIN SCORE

Score	Definition¹
0	No observed neurological symptoms
1	No significant neurological disability despite symptoms; able to carry out all usual duties and activities
2	Slight neurological disability; unable to carry out all previous activities, but able to look after own affairs without assistance
3	Moderate neurological disability; requiring some help, but able to walk without assistance
4	Moderate severe neurological disability; unable to walk without assistance and unable to attend to own bodily needs without assistance
5	Severe neurological disability; bedridden, incontinent and requiring constant nursing care and attention as a result of a neurological deficit
6	Dead

¹ van Swieten J, Koudstaal P, Visser M, Schouten H, *et al* (1988). "Interobserver agreement for the assessment of handicap in stroke Subjects". *Stroke* **19** (5): 604-607

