8.14.2 Six Minute Walk Test

Subjects may not be able to walk due to heart failure, especially at baseline. Subjects unable to walk due to heart failure will receive a score of 0 meters. For all other reasons for missing data the score will remain missing and not be included in the analysis. The Six Minute Walk test will be conducted at baseline and then at months 3, 6, 12, 18 and 24 post implant. Data will be analyzed using mixed modeling by comparing the distances walked over time to the baseline distance. The Short Term indication will be limited to the 3 and 6 month assessment. The long term indication will include all assessments until 24 months or outcome, whichever occurs first.

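### The six-minute walk analysis leaves out inability to walk caused by stroke or another complication; a second analysis scoring it 0 m should be prespecified

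*Protocol*

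**What the plan says.** The scoring rule is the same in both documents. SAP 8.14.2 states: "Subjects unable to walk due to heart failure will receive a score of 0 meters". Protocol 13.15.2 continues: "For all other reasons for missing data the score will remain missing and not be included in the analysis". The model is given as "Data will be analyzed using mixed modeling by comparing the distances walked over time to the baseline distance".

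Other provisions bear on the rule:

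- Protocol 13.14 (SAP 8.13 agrees): "There will be no imputation of missing data for the secondary endpoints".
- Protocol 16.7.1, with matching items in 16.2 and 16.7.2, lists "6 Minute Walk Test (6MWT) (if Subject is able; reason must be provided if not performed". The cause of a missing test is therefore on record.
- Protocol Appendix 4, for a test begun and not finished: "Record the distance completed, the time the test was stopped and the reason for pre-maturely stopping". Such a test yields a distance and is not missing.
- Protocol Appendix 5 defines a modified Rankin Score of 4, the first level that fails the primary endpoint, as "Moderate severe neurological disability; unable to walk without assistance and unable to attend to own bodily needs without assistance".
- Protocol 8 and 22: follow-up runs to 24 months or to transplant, explant or death. Stroke is neither an outcome nor a listed reason for withdrawal.

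Neither document specifies a sensitivity analysis for the scoring rule.

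**The concern.** The 0 m rule recognises that a subject too ill to walk has a very low walking capacity, not an unknown one. It applies that reasoning to one cause only. A subject alive on the pump who cannot walk after a disabling stroke, or because of another complication, is handled like someone who missed the visit for a scheduling reason. The mixed model then treats the gap as ignorable and in effect assumes that the subject would have walked about as well as comparable subjects.

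Functional status is a named secondary objective and endpoint (Protocol 9.2 and 10.2), and each secondary endpoint is tested at two-sided 0.05 (Protocol 13.14, SAP 8.13). Two results are at stake. One is the gain from baseline in each arm. The other is the between-arm comparison, should one device leave more survivors unable to walk for reasons other than heart failure.

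Attribution adds to this. The trial is unblinded. The protocol asks for an independent assessor for NYHA class and the modified Rankin Score, but states no such requirement for deciding whether heart failure is why a subject could not walk. That decision moves a value between 0 m and exclusion.

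**Working it through.** **No plan figure to reproduce.** The documents give no sample size, power, expected distance or standard deviation for the walk test. All distances and shares below are assumptions.

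**Step 1: who is affected.** Take a subject with a modified Rankin Score of 4 after a stroke, alive on support. The subject stays on the visit schedule. If the test is not done because of the stroke, the recorded reason is not heart failure, so 13.15.2 and 8.14.2 leave the value missing and 13.14 and 8.13 bar imputation. Tests at earlier visits stay in the model.

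**Step 2: effect on an arm mean.** Let q be the share of subjects alive on support who cannot walk at a visit for a medical reason other than heart failure, and m the mean distance of the rest.

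- Planned rule: mean = m
- Inability scored 0 m: mean = (1 − q) × m
- Excess under the planned rule: q × m
- Between-arm difference hidden: m × (q in HM II − q in HM3)

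**Step 3: illustration with m = 300 m.**

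| q HM3 | q HM II | Excess HM3 | Excess HM II | Difference hidden |
|---|---|---|---|---|
| 3% | 6% | 9 m | 18 m | 9 m |
| 3% | 10% | 9 m | 30 m | 21 m |
| 6% | 6% | 18 m | 18 m | 0 m |

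For m from 200 to 400 m, the 3% v 6% case hides 6 to 12 m and the 3% v 10% case 14 to 28 m. Over q from 2% to 15% and the same range of m, the excess in one arm runs from 4 m (0.02 × 200) to 60 m (0.15 × 400).

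**Step 4: does the mixed model repair it?** This was checked by simulation with 183 subjects per arm, visits at baseline and months 1, 3 and 6, and a random-intercept model with visit, arm and their interaction, in 40 replicates. Assumed inputs were: 40% scored 0 m at baseline for heart failure; means of 150 m for baseline walkers and 200, 280 and 300 m at months 1, 3 and 6; between- and within-subject SD of 70 m each; and onset of inability spread evenly over six months. The 6-month results for HM3 minus HM II change from baseline were:

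| q HM3 v HM II | Planned rule | Inability = 0 m | Shift |
|---|---|---|---|
| 3% v 6% | −3.5 m | +5.8 m | 9.3 m |
| 3% v 10% | −0.5 m | +19.7 m | 20.2 m |
| 6% v 6% | +1.1 m | +0.2 m | −0.9 m |

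The simulation standard error of each difference is about 2 m. The shifts agree with the 9, 21 and 0 m from the formula, so keeping the earlier visits in the model does not remove the effect. In the 6% v 6% case the within-arm changes were 209.0 and 210.1 m under the planned rule, against 192.1 and 192.4 m with inability at 0 m. Each arm's gain is inflated by about 17 to 18 m even with no between-arm bias.

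**The case against.** The strongest reply is that the rule is a deliberate and consistent choice. For a heart-failure device, counting only cardiac inability as 0 m can be defended, and a value is inflated only relative to a strategy that also counts other medical inability. This stands. It is why the rule is not called an error, and why a second analysis is asked for rather than a replacement. It does not make the excluded values ignorable.

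Four stronger readings are tempting, and the documents do not support them:

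- *The comparison is biased.* That needs unequal rates of such inability, and the documents give none. The sponsor's expectation of less thrombus and fewer pump replacements with HM3 (Protocol 13.5.1) makes unequal rates plausible, but no more than that.
- *Most inability after implant is excluded.* Protocol Table 1 also allows right heart failure in up to 23% at 6 months and 25% at 24 months. Inability from that cause could plausibly still score 0 m.
- *Table 1 gives the size.* Its 12% and 19% are upper bounds for all strokes, not for disabling strokes in survivors.
- *Every subject with a disabling stroke vanishes from the functional results.* Only tests not performed are lost. Appendix 4 does not expressly bar an assisted walk, and NYHA class, EQ-5D-5L and KCCQ remain scheduled.

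It is also fair to say that the walk test is unpowered and that the SAP (Section 7) disclaims statistical claims on secondary endpoints. That limits the consequence. Finally, scoring 0 m for a passing illness is open to debate, and neither rule deals with death.

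**Conclusion.** The point holds as a cheap improvement to a secondary analysis. Both documents exclude walk tests not performed because of stroke or another adverse event in subjects alive on support. That exclusion is informative, and the planned mixed model does not correct it. It raises each arm's mean by the share unable times the walkers' mean, and distorts HM3 versus HM II by the difference in shares times that mean.

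At an assumed 300 m, this is about 9 m for 3% v 6% and about 21 m for 3% v 10%. With equal shares the between-arm difference stays near 0 and only the change from baseline is inflated. Neither the direction nor the size in this trial can be derived from the documents. The primary endpoints and the powered pump-replacement comparison are unaffected.

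**What to change.** Prespecify a companion analysis in Protocol 13.15.2 and SAP 8.14.2. It scores 0 m for any subject alive on support whose test was not performed because heart failure, stroke or another adverse event made them unable to walk. Only non-medical reasons, such as a missed visit or a refusal, stay missing. Report it beside the heart-failure-only analysis, and tabulate the reasons for non-performance by arm and visit.

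The cost is a few sentences in each document, one more model run and one table. No new data are needed, because the reason for a test not done is already required. The drawbacks are more zeros, a more skewed outcome and a less favourable mean change. Someone must also judge, in an unblinded trial, whether a recorded reason is medical.

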13.16 Analysis of Quality of Life

Quality of Life will be measured using the EuroQol (EQ-5D-5L) and the Kansas City Cardiomyopathy Questionnaire (KCCQ).

13.16.1 EQ-5D-5L

The EQ-5D-5L VAS and total score will be assessed at baseline and then at 1, 3, 6, 12, 18, and 24 months. Data will be analyzed using mixed modeling by comparing the EQ-5D-5L score at each assessment interval to the baseline score. The Short Term indication will be limited to the 1, 3, and 6 month assessments. The Long Term indication will include all assessments until 24 months or outcome, whichever occurs first. In addition, the percentage of each component of the EQ-5D-5L will be graphically presented over time.

13.16.2 KCCQ

The KCCQ score will be assessed at baseline and then at 3, 6, 12, 18, and 24 months. Data will be analyzed using mixed modeling by comparing the KCCQ score at each assessment interval to the baseline score. The Short Term indication will be limited to the 3 and 6 month assessments. The Long Term indication will include all assessments until 24 months or outcome, whichever occurs first.

13.17 Powered secondary analysis:

In addition to the primary outcome, the study will be powered to test if HM3 pump reliability is superior to HM II by analyzing the incidence of pump replacements. Randomization described in Section 13.4 will continue beyond the Subjects needed to power the primary endpoint until a sufficient sample size has been enrolled to test the secondary endpoint. The null and alternative hypotheses are:

$$H_0: \pi_{HM3} \geq \pi_{HM II}$$

$$H_A: \pi_{HM3} < \pi_{HM II}$$

where π_{HM3} is the HM3 pump replacement rate and $\pi_{HM II}$ is the HM II pump replacement rate.

Based on data contained in Thoratec's device tracking database, 7% of the HM II Subjects receive a pump replacement by 24 months. If we assume that HM3 pump replacements will be reduced to 3% at 24 months, then 1028 Subjects will be needed to prove superiority with a power of 80% and alpha = 0.05 (2-sided).

Once the 366 Subjects needed for the long term indication are enrolled, Thoratec will continue to randomize 662 more Subjects for this secondary analysis. Data for this secondary analysis is not needed for the short or long term indications, but rather will be used to provide additional labeling information.

The Subjects will be followed for 24 months or to outcome, whichever occurs first, and analyzed using the Fisher's exact test. Treatments will also be compared on time-to-pump replacement using the log-rank test where Subjects without a replacement are censored at last known follow-up. Otherwise, there will be no imputation of missing data for this analysis.

14 ADVERSE EVENTS (AE)

14.1 Adverse Events

Adverse Events are any unfavorable and unintended sign (including abnormal labs), or symptom or disease temporally associated with the investigational product and whether or not related to the use of the investigational product. Investigators are responsible for reporting required pre-defined AEs to the Study Sponsor in a timely manner by submitting AEs through the EDC, and for reporting AEs to their Institutional Review Board (IRB) as required.

All pre-defined, anticipated AEs, including those occurring after discharge, will be reported and will be categorized as related to the device or not.

All anticipated AE definitions can be found in Appendix 1.

14.2 Serious Adverse Event (SAE)

Serious adverse events are defined as those adverse events causing death, or congenital abnormality or birth defect, or a life-threatening illness or injury that results in permanent disability, requires hospitalization, or prolongs a hospitalization, and/or requires intervention to prevent permanent injury or damage.

SAEs must be reported to the Sponsor by submitting through the EDC as soon as possible but no later than three (3) calendar days from the day the study personnel became aware of the event or as per the investigative site's local requirements, if the requirement is more stringent. The date the site staff became aware that the event met the criteria of a serious adverse event must be recorded in the source document. The Investigator will further report the SAE to the local IRB according to the institution's IRB reporting requirements.

All SAEs will be reported and will be categorized as related to the device or not.

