13.10 Analysis of Adverse Events

All pre-defined adverse events will be captured. Tables will be created for HM3 and HM II AEs that show the by-treatment incidences of all adverse events and the by-treatment event rate per patient year of support. Serious adverse events (SAEs) will be analyzed in a similar manner as AEs. Differences in event rates between the treatment arms will be analyzed using Fisher's Exact test or Poisson regression, as appropriate.

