APPENDIX 1: ANTICIPATED ADVERSE EVENT DEFINITIONS

Bleeding

An episode of SUSPECTED INTERNAL OR EXTERNAL BLEEDING that results in one or more of the following:

- a. Death,
- b. Reoperation,
- c. Hospitalization,
- d. Transfusion of red blood cells as follows:
 - If transfusion is selected, then apply the following rules:

During first 7 days Post-implant

- ≥ 50 kg: ≥ 4U packed red blood cells (PRBC) within any 24 hour period during first 7 days post-implant.
- <50 kg: ≥20 cc/kg packed red blood cells (PRBC) within any 24 hour period during the first 7 days post-implant

After 7 days Post-implant*

- Any transfusion of packed red blood cells (PRBC) after 7 days following implant with the investigator recording the number of units given. (Record number of units given per 24 hour period).

Note: Hemorrhagic stroke is considered a neurological event and not as a separate bleeding event.

*Any transfusion of ≥ 2U packed red blood cells (PRBC) after 7 days following implant will be considered a serious bleed

Cardiac Arrhythmias

Any documented arrhythmia that results in clinical compromise (e.g., diminished VAD flow, oliguria, pre-syncope or syncope) that requires hospitalization or occurs during a hospital stay. Cardiac arrhythmias are classified as 1 of 2 types:

- 1) Sustained ventricular arrhythmia requiring defibrillation or cardioversion.
- 2) Sustained supraventricular arrhythmia requiring drug treatment or cardioversion.

Pericardial Fluid Collection

Accumulation of fluid or clot in the pericardial space that requires surgical intervention or percutaneous catheter drainage. This event will be subdivided into those with clinical signs of tamponade (e.g. increased central venous pressure and decreased cardiac/VAD output) and those without signs of tamponade.

Device Malfunctions

A Device Malfunction occurs when any component of the MCS system ceased to operate to its designated performance specifications or otherwise fails to perform as intended. Performance specifications include all claims made in the Instructions for Use.

Internal Component Malfunction: Malfunction of any device system component that is implanted within the patient. A malfunction to these components may require further surgery to repair or replace.

External Component Malfunction: Malfunction of a device system component that is used external to the patient and can be replaced or repaired without the need for further surgery.

Device Thrombosis

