8.9 Analysis of Adverse Events

All pre-defined adverse events will be captured. Tables will be created for HM III and HM II AEs that show the by-treatment incidences of all adverse events and the by-treatment event rate per patient year of support. Serious adverse events (SAEs) will be analyzed in a similar manner as AEs. Differences in event rates between the treatment arms will be analyzed using Fisher's Exact test or Poisson regression, as appropriate.

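### As printed, Section 14.2 makes admission, disability and intervention conditions on a life-threatening event, so non-life-threatening admissions may be graded inconsistently as SAEs

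*Protocol*

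**What the plan says.** Protocol Section 14.2 contains the only general definition of seriousness in the two documents. It opens: "Serious adverse events are defined as those adverse events causing death, or congenital abnormality or birth defect, or a life-threatening illness or injury". It continues: "that results in permanent disability, requires hospitalization, or prolongs a hospitalization, and/or requires intervention to prevent permanent injury or damage". The words that matter here run across that join: "a life-threatening illness or injury that results in permanent disability, requires hospitalization, or prolongs a hospitalization". An event graded serious must reach the sponsor "no later than three (3) calendar days from the day the study personnel became aware of the event". For other events, Section 14.1 sets no number of days: "Investigators are responsible for reporting required pre-defined AEs to the Study Sponsor in a timely manner".

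Seriousness also decides what is analysed. Protocol Section 13.10 states "Serious adverse events (SAEs) will be analyzed in a similar manner as AEs". SAP Section 8.9 repeats this and names the comparison: "Differences in event rates between the treatment arms will be analyzed using Fisher's Exact test or Poisson regression, as appropriate". The SAP has no SAE definition of its own.

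Two other places bear on what serious means. In Protocol Appendix 1, under Bleeding, a footnote says that a transfusion of 2 or more units of packed red cells "after 7 days following implant will be considered a serious bleed". Protocol Section 15, on unanticipated adverse device effects, lists a serious effect, a life-threatening problem and death as alternatives to one another.

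**The concern.** An SAE definition normally lets a reader tick any one of several outcomes. Here several of those outcomes sit inside a clause that describes a life-threatening illness or injury. A site that follows the sentence would not grade an admission for a driveline infection as serious unless it judged the infection life-threatening. A site that takes admission as sufficient would grade it serious.

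Two things depend on the answer. The first is timing, since only an SAE starts the 3-day clock. The second is the SAE comparison between arms, because a count is hard to interpret if its case definition varies from site to site. The trial allows up to 70 sites, and the visit sections (16.3 and 16.5 to 16.7) have the site record seriousness for each AE.

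**Working it through.** No arithmetic applies. The check is how the sentence parses, and whether the rest of the plan agrees with that parse.

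1. **Grammar.** The sentence names three things an adverse event may cause: death, a congenital or birth anomaly, or a life-threatening illness or injury. The relative clause follows the third. Its verbs (results, requires, prolongs, requires) are singular. They agree with illness or injury, not with the plural adverse events at the start. So disability, new admission, prolonged stay and intervention all qualify the life-threatening illness or injury.

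2. **What follows literally.** A non-life-threatening event that needs admission is not serious. In addition, a life-threatening event is not serious unless it also meets one of the trailing conditions.

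3. **The readings side by side**, for events that cause neither death nor a birth anomaly:

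| Illustrative event | 14.2 as printed | 14.2 read as separate criteria | Appendix 1 |
|---|---|---|---|
| Driveline infection, admitted, not life-threatening | Not serious | Serious (admission) | No seriousness rule given |
| Bleed after day 7, admitted, 1 unit given, not life-threatening | Not serious | Serious (admission) | An AE, not called serious |
| Bleed after day 7, 2 units given, no new or prolonged admission, not life-threatening | Not serious | Not serious, unless the transfusion counts as preventive intervention | Serious |
| Life-threatening event meeting none of the trailing conditions | Not serious | Serious | Depends on event type |

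The first two rows show an event changing status with the reading. The third shows a direct conflict between 14.2 as printed and Appendix 1. It also shows that separating the criteria does not by itself settle how the bleed rule relates to an SAE.

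4. **Section 15.** Listing serious and life-threatening as alternatives would be odd if every serious non-fatal event (birth anomalies aside) already had to be life-threatening. This is a poor fit with 14.2, not a contradiction.

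5. **Any overriding rule?** Neither document gives a second general definition, or says which rule prevails when 14.2 and Appendix 1 differ.

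6. **What the definition does not touch.** All pre-defined AEs are tabulated and compared whatever their seriousness (Protocol 13.10, SAP 8.9). Time to rehospitalization and time to reoperation are compared by log-rank test (Protocol 13.14.3 and 13.14.4). The primary composite and the 24-month pump-replacement endpoint make no use of SAE status.

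**The case against.** The strongest reply is that the sentence is a list flattened by poor punctuation. Read strictly it gives an implausible result for some life-threatening events, while Appendix 1 and Section 15 both point to a broader intent. Many sites will therefore treat admission as enough. This stands as far as intent goes, and it means that one cannot say how sites actually grade. It does not remove the point: a protocol should not depend on sites departing from its wording, and mixed readings are what make the SAE count inconsistent.

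A reader might infer more than the documents support, in three ways.

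- **That safety information is lost.** It is not. The events remain in the all-AE, rehospitalization and reoperation analyses. The DSMB is to receive all safety data at its early review, not only SAEs (Section 31.1.1). What can be lost is the 3-day deadline and the SAE classification. One partial gap remains: the rehospitalization analysis cannot identify an event that prolonged the implant stay.
- **That the comparison between arms is biased.** Randomization is stratified by center and blocked 1:1, so a site's habitual reading applies to both arms. The trial is unblinded, but the documents show no mechanism that would push the reading in one direction by arm. An independent committee adjudicates the categorization of AEs (Section 31.1.2). Nothing in the documents says whether that includes seriousness, and its charter is not available, so neither answer can be assumed.
- **That a count of misgraded subjects can be derived from Table 1.** The 6-month figures there, 56% for bleeding and 26% for driveline infection, are ceilings taken from upper 99% confidence limits in HM II post-approval studies. They are not expected rates. The bleeding figure also mixes in transfusions during the first 7 days and late bleeds that Appendix 1 already calls serious. No document gives the share of events that lead to admission without threatening life.

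**Conclusion.** The point holds as a defect in the printed rule. Section 14.2 makes disability, admission, prolonged stay and intervention conditions on a life-threatening illness or injury. Followed literally, this keeps non-life-threatening admissions out of the 3-day report and the SAE table. It conflicts with the Appendix 1 bleed rule and sits badly with Section 15, so sites can grade the same event differently.

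The reach is limited to reporting time and to one safety tabulation. SAP Section 7 says that no statistical claims will be made on secondary endpoints, and neither the primary nor the powered secondary endpoint is affected. The number of events involved cannot be estimated from the documents, and a definite under-count of SAEs cannot be asserted, because it depends on how sites read the sentence. The conclusion rests on the text of both documents; the eCRFs, their completion guidelines and the committee charters could contain a clarification that is not visible here.

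**What to change.** - **Rewrite Section 14.2 as a list in which each item is sufficient alone:** death; life-threatening; permanent disability; new or prolonged hospitalization; intervention to prevent permanent injury or damage; congenital abnormality or birth defect.
- **Reconcile Appendix 1 and Section 15 with that list.** State explicitly whether every Appendix 1 serious bleed is an SAE, since the list alone does not decide it. Have SAP Section 8.9 refer to the same definition.
- **Check what has already been recorded.** Query AEs graded non-serious against the rehospitalization and operative-procedure records that Table 2 of the Protocol already collects, using one rule in both arms. Those records do not show an event that prolonged the implant stay, so that criterion needs a query to the site.

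The text change is about one paragraph plus cross-references. The real cost is the query work in both arms and some additional 3-day reports from sites.
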